# **LIST OF ABBREVIATIONS**

BASR	Board of Advanced Studies and Research
C.I	Confidence Interval
CONSORT	Consolidated Standards of Reporting Trials
DUHS	Dow University of Health Sciences
DASS	Depression, Anxiety and Stress Scale
ECT	Electroconvulsive Therapy
IRB	Institutional Review Board
IRD	Interactive Research and Development
MBT	Multimedia Booklet and Telephone
MRI	Magnetic Resonance Imaging
n	Number of samples /Participants selected
NCCN	National Comprehensive Cancer Network (NCCN)
NCSS	National Council for the Social Studies
PASS	Primary Avionics Software System
NIH	National Institutes of Health
O.R	Odd Ratio
P-Value	Probability Value
QOL	Quality of Life
RCT	Randomized control Trial
RM ANOVA	Repeated Measure Analyses of Variance
SPSS	Statistical Package for the Social Sciences
STAI	State-Trait Anxiety Inventory
USA	United State of America

#### ABSTRACT

#### **Background:**

A wide range of pediatric cancers are treated by chemotherapy. The adverse effects are usually managed by their parents at home. Ineffective coping and lack of knowledge about chemotherapy side effect management leads parent's psychology disorders. Contemporary research evidence that Nurse-led education, booklet providence and follow up about chemotherapy and side effect management, help to decrease parent's anxiety and depression.

#### **Objectives:**

To measure the effect of nurse-led multimedia education, booklet providence and telephonic follow up about chemotherapy and side effects management on parent's anxiety, depression and stress of children receiving chemotherapy for the first time.

#### Methodology:

A randomized control trial was conducted in the department of chemotherapy at Department of Pediatric Oncology at Indus hospital, Karachi from September-December 2018 on parents of children below 18 years of age undergoing chemotherapy for the first time. Total 100 parents were randomly divided into Intervention group (n=50) and Control Group (n=50). After excluding lost to follow up, the data was analyzed from 77 sample of parents (41 in intervention group and 36 in control group). The intervention group received multimedia education, booklet and weekly tele-nursing follow-up about chemotherapy and side effects management. The control group received routine care. Parent's anxiety, depression and stress were identified by using DASS-21 and repeated measures ANOVA was used to observe changes in outcomes over study period.

#### Result

Total 63.4% (n=48) children were under 12 years of age and 64.9% (n=50) children were male. Majority of the parents were non-residence of Karachi, labor and low education and income. 66.2% (n=51) children diagnosed with leukemia, 63.6% (n=49) children had no pain. At the baseline, depression was found in 84.4% (n=56) parents while 67.5% (n=52) parents were anxious and 55.8%(n=43) parents had stress, After the MBT intervention, significant reductions were observed in depression and stress (P-Value <0.05) of the parents in MBT group. A sharp decline was observed just after one week while at final stage intervention group showed higher decrease in depression and stress while anxiety was observed insignificantly different in both groups,

#### **Conclusion:**

There is a positive effect of nurse-led multimedia education, booklet providence and telephonic follow up about chemotherapy and side effects management on parent's depression and stress of children receiving chemotherapy showing in this study for the first time in Pakistan. For anxiety reduction, other strategies should also be incorporated.

#### **Keywords:**

Nurse-led, Multimedia education, Booklet, telephonic follow-up, chemotherapy, side effects, parents, anxiety, depression, children, cancer

# Registered: www.clincaltrials.gov (NCT03753542)

**CHAPTER 1: INTRODUCTION** 

### 1.1 Background

#### Children Cancer in Pakistan:

Millions of people are affected by cancer worldwide. Cancer is one of the major health problems in Pakistan [1, 2]. According to W.H.O in male, 61,624 incidence cases, 42,624 cancer deaths and in female 75,095 incidence cases and 43,188 deaths reported annually worldwide. About 8,000 children below 18 years are diagnosed with cancer annually. Most children diagnosed in advanced stage [2]. In Pakistan, 31% children have leukemia, 20% have Lymphoma, 08 % have sarcoma, 8 % have bone tumor, 7% have brain tumor, 6 % have retinoblastoma, 5 % have Wilms tumor, 4% have germ cell tumor, 4 % have neuroblastoma and the rest 7 % have other types of cancer [2, 3].Cancer affects families emotionally and physically. [4, 5]

# Chemotherapy and side effect:

Large number of cancer patient face difficulties due to chemotherapy worldwide. If the patient was not prepared properly for chemotherapy treatment,, he/she could face problem in coping with and managing the side effects of chemotherapy.[6]. Chemotherapy is the common method of treatment for cancer management [7]. The common side effects of chemotherapy as reported in literature include diarrhea, nausea and vomiting, hair loss, neuropathy, weight loss, dysphagia, oral ulcer, fatigue, dyspnea, constipation, insomnia and cognitive impairment [8-13]. It also affects quality of life, economic conditions, emotions and social wellbeing [7, 12-14]. As reported in literature, before starting chemotherapy treatment, the patient should receive written information about diagnosis, treatment goal, chemotherapy duration and side effects of drugs, and the material should be design at the level of patient knowledge.[15]

#### Anxiety, Depression & Stress:

The prevalence of anxiety is high among cancer patient due to unawareness about chemotherapy's side effect. 47% of cancer patient undergoing chemotherapy have anxiety due to chemotherapy [16]. The power to control disease can be lost because of anxiety [17]. Side effect of chemotherapy management required self-care and this capability of patient can be effected due to depression.[18]. Anxiety and depression had an association with cancer, chemotherapy related fatigue, lack of education about chemotherapy side effect management and long term exposure of children in hospital [4, 11, 19-21]. Cancer treatment requires nursing intervention to reduce anxiety and depression [4, 22]. Anxiety leads to delay chemotherapy treatment and prognoses [11, 23].

## Evidences of Multimedia education to reduce Anxiety and depression:

This is the main responsibility of oncology nurse to educate patient about the management of side effect of chemotherapy but most patient received only written material instead of proper education regarding management of chemotherapy side effects [11, 18, 24-26]. The recommended practice to reduce anxiety of patient is to educate the patient about the side effects of chemotherapy. The patients should be educated both for short term management and long-term management. Education about side effects of chemotherapy helps the patient in decreasing their anxiety[27, 28]. The effect of multimedia education to reduce anxiety is evident in mammography, MRI, ECT, cardiac surgeries, gynecological laparotomy, laparoscopic cystectomy, hemodialysis, teeth removal and peptic ulcer disease.[23, 29-45]. Nursing intervention through education helps to reduce anxiety and stress [8, 9, 19, 20], after chemotherapy, promote side effect management, decrease complications and increase psychological wellbeing. [11, 15, 16, 46]. Many resource materials are available on internet for

patient education on cancer about chemotherapy and its side effects, and to enhance the psychosocial health of cancer patients. These resources can be utilized as a part of continuous nursing education [11, 16].

#### Anxiety and depression in Pakistan:

Anxiety and depression are common psychological disorders in Pakistan due to lack of resources and proper infrastructure for mental health services [4].

#### Aim of the study:

The aim of this study is to determine the effects of nurse led chemotherapy education on parent's anxiety and depression, as parents have the key role in caring their children cancer. This study helped to examine the effects of psycho-education about chemotherapy and its side effect management on parent's anxiety, depression and stress at Department of Pediatric Oncology at Indus hospital, Karachi Pakistan.

#### 1.2 Statement of Problem

The prevalence of cancer among children has been projected drastically since last decades in Pakistan [1, 2]. Children cannot look after themselves. Parents are the primary caregiver of children [5, 21, 47]. If they initially feel anxiety and depression, it is difficult for them to manage chemotherapy and side effects [5, 11, 15, 47-49]. Education about chemotherapy has been neglected due to heavy workload and other responsibilities of duty nurses [11, 15, 50]. More than 50% of individual newly diagnosed with cancer have unknown anxiety related to chemotherapy and their side effect [51]. As per literature, those who do not receive chemotherapy education prior to treatment face difficulties in later life [6]. The side effects of chemotherapy, like vomiting, nausea, loss of appetite and fatigue were managed through self-care [52]. After an intensive literature review it was found that no study has been conducted in Pakistan focusing on effect of nurse-led multimedia education and telephonic follow up on chemotherapy side effects management for parent's anxiety and depression.

#### **1.3 Rationale of Study**

Pediatric cancer is the leading cause of children mortality and morbidity in Pakistan. More than 8,000 children under 18 years of age are diagnosed with cancer in a year. Cancer treatment are managed by the parents, usually by the mothers of children [5, 21]. Evidences showed lack of knowledge about chemotherapy and dissatisfaction of the information about what they had received leads to uncertainty, apprehension and delay continuation with chemotherapy treatment [4, 11, 15, 52]. Many organizations have developed booklet for patient's education about chemotherapy and side effect management. They have also provided online resources. The patient read the information using their own efforts [11, 16, 29-37]. Multimedia education and Tele-nursing follow up are reported as cost effective method to reduce family anxiety in many countries [11, 23, 25, 26, 29-46, 51, 53, 54]. Parent's anxiety and depression lead to poor management of cancer treatment for their child. Literature reveals that Nurse led psycho-education through multimedia education and telephonic follow up was found cost effective method to reduce anxiety and depression related to treatment process. According to a senior oncologist in Pakistan, parents are anxious not only about chemotherapy side-effect but also about the disease itself [2]. Most parents have the same knowledge of side effects of chemotherapy as they experienced with friend's relatives who had undergone to course treatment. Secondly, side effect was mentioned at first counseling session by primarily oncologist.

#### 1.4 Objectives

To measure the effect of nurse-led multimedia education, booklet providence and telephonic follow up about chemotherapy and side effects management on parent's anxiety, depression and stress of children receiving chemotherapy for the first time

# **1.5 Research Question:**

Are there effects of nurse-led multimedia education, booklet providence and telephonic follow up about chemotherapy and side effects management on parent's anxiety, depression and stress of children receiving chemotherapy for the first time?

# **1.6 Operational Definitions**

**Depression**: The score greater than 9 under DASS-21 scale Criteria **Anxiety**: The Score Greater than 7 under DASS-21 scale Criteria **Stress**: The Score Greater than 14 under DASS-21 scale Criteria

#### **CHAPTER 2: LITERATURE REVIEW**

#### 2.1 International Findings:

European literature reported that 20 minutes of video education was more effective than verbal and written education [55]. A randomized control trial was done by Williams and Schreier (2005), the experimental group (n=38) received audiotaped 20 minutes of education on management of fatigue, sleep disturbance and anxiety along with standard care and the control group (n=33) received verbal instruction and written material. The anxiety level was measured at 1 month and 2 months. More number of patient (n=16) in control group reported anxiety as compared to experimental group (n=10) significantly (p=0.001) [26] Similar results were found from the study of Malone (2007) that education helps to reduce anxiety. Another study mentioned that familiarity with environment of chemotherapy was necessary as it has also an impact on anxiety [11, 56]. Almost 50% cases diagnosed with cancer reported the symptoms of anxiety [51]. According to NCCN guideline, the anxiety management related to chemotherapy and side effect management was the primary responsibility of oncology team including oncology nurse [16]. Study from USA mentioned that the caregiver of children diagnosed with cancer had 44% greater stress as compared to 24% parents of healthy children [47]. Another study mentioned that 98% participant were satisfied with chemotherapy educational experience, all study participants found educational environment as supportive and 81% felt that quality of life could be improved through education [46]. Another study mentioned 87.6% participant were satisfied with chemotherapy education, 87.5% agree that it helps to reduce anxiety, 93.3% participant felt that it was effective if given first time before chemotherapy, 86.6% participant was satisfied for 30 minutes of education timing before chemotherapy treatment. 85.7% participant report that quite room environment was effective for chemotherapy education [11]. In another study 84% patient reported that educational class was a help to reduce anxiety and 64.7% participant disagree for education in group [25]. A randomized control trial was

conducted in Greenville and concluded that 23% participant in control group reported anxiety after 1 month of treatment as compared to 14% in interventional group [26]. Written information before chemotherapy should be provided to patient, the information should include chemotherapy and side effect, future plan, and follow-up [15]. Many studies had mentioned that that psycho-education was effective to reduce anxiety during chemotherapy management [28, 51, 56, 57].

#### 2.2 Regional Finding

A study from Korea mentioned 38% (n=342) caregiver of children bearing cancer had anxiety, with 5 % of them had severe anxiety. 82% (n=737) caregiver had depression, and 16% abode severe depression of cancer patient. The predicted anxiety level of family caregiver was 9.22 times higher with poor Quality of life (QOL), for burdensomeness 3.44 times higher for degree of disturbance and 2.12 times higher for financial concerns. There are many evidences of nursing intervention effect on anxiety and depression other than chemotherapy side effect management. A study from Turkey mentioned the effect of multimedia nursing education for cardiac care on anxiety and depression score from  $6.1\pm0.7$  and  $5.4\pm0.6$  reduced to  $1.9\pm0.2$ and  $1.9 \pm 0.3$  [37]. In Iran effect of nurse led telephonic follow on anxiety and depression for hemodialysis patients was studied [42] Other studies provided evidences of family anxiety reduction in cardiac care [23, 29, 34, 38], during electroconvulsive therapy [33], elderly care [22] and for laparoscopic cholecystectomy [41].. Another study from Korea also mentioned the effect of nursing intervention on anxiety during laparoscopy hysterectomy [58]. A study from Azerbaijan mentioned positive effect of nursing intervention on anxiety during endoscopy [53] and from Egypt mentioned positive effect of nursing intervention on anxiety during MRI procedures [32]. Studies from China also mentioned the effect of nursing intervention on anxiety level for peptic ulcer [44], breast cancer [40], tooth extraction [43] and laparotomy [39].

#### 2.3 Local findings:

A study from Rawalpindi revealed that 10%-25% participant reported anxiety and depression during chemotherapy and 16% had anxiety and 27% had depression [4]. Myeloid leukemia was commonly diagnosed in younger age but mostly reported in chronic phase [59]. A study from Lahore mentioned that 56% parents had depression, higher in mothers specially those who were low educated and had poor socio-economic class [5]. A study from Karachi mentioned caregiver stress related to cancer patients, 17% mild, 34% moderate and 49% had severe stress. It was also concluded that caregiver stress for cancer patient had significant association with caregiver age, relationship with child, female gender and longer duration of care [49]. A study was conducted in Karachi to identify the psychological need of parents of children disposed with cancer and found that correct and adequate information through education is necessary for parents [60].

We fail to find study both regional and locally focusing this concept.

## **CHAPTER 3: METHODS AND MATERIALS**

#### 3.1 Study Design:

Randomized control trial (RCT)

#### 3.2 Study Setting:

Department of Pediatric Oncology at Indus hospital, Karachi

# 3.3 Study Duration:

September 2018 to December 2018

#### 3.4 Study Population:

The populations of interest were parents along with their children receiving chemotherapy treatment for the first time.

# 3.5 Inclusion criteria:

- 1. Parents along with their children younger than 18 years of age
- 2. Parents along with their children newly diagnosed with cancer in last three weeks
- 3. Parents along with their children schedule to receive first time chemotherapy in the outpatient department

# 3.6 Exclusion Criteria

- 1. Parents along with their children refused to participate
- 2. Parents along with their children already receiving interventions like multimedia education, booklet providence and telephonic follow up for chemotherapy and side effect management
- Parents taking medicine for their anxiety and depression. (e.g. Anxiolytics/ Antidepressant)
- 4. Parents showing uneasiness and discomfort during educational session.

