#### 3.8 Sampling Technique:

Samples were randomly drawn by using block randomization list. This allocation was based on computer generated random allocation with randomly selected size of block i.e. number of patients on a given day. The participation of each parent in each session was based on the given generated numbers. For example, if on a given day block of parents was recommended by the consultant to the researcher then based on generated block random number; parents were allocated to either intervention arm or control arm. The same procedure was repeated on other day until the sample size in each group was completed. This sampling technique was referred as stratified random sampling.

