#### 3.9 Data Collection Procedure:

- Approval: Being a part of academic research, approvals were taken from scientific committee, institutional review board (IRB) and Board of Advanced Studies and Research (BASR) of Dow University of Health sciences, Karachi. Then ethical review committee of Research Department, Indus hospital Karachi was obtained where the study participants were approached.
- 2. **Multimedia Room arrangement**: A room was arranged for multimedia chemotherapy education.
- 3. **Approach to target population**: The target population was approached through Pediatrics oncology registration counter. A help was also taken from the primary adviser to acknowledge each newly advised chemotherapy children along with their parents to Multimedia education room.
- 4. **Parent selection:** In the multimedia room, consent was taken from the parents and they were selected according to the above-mentioned inclusion and exclusion criteria.
- 5. **Randomization:** The parents were allocated to Intervention group and Control group per the generated random number as mentioned in sampling technique defined in section 3.8.
- 6. Socio-demographic and others information: The socio-demographics and others information were collected as given in Annexure -1.
- Pre-Intervention Anxiety, Depression and stress: Parent's anxiety, depression and stress levels were assessed by using DASS-21 (Urdu version) as mentioned in Annexure –II.
- 8. **Post-intervention Anxiety, Depression and stress:** After two weeks the anxiety, depression and stress levels were again assessed by using DASS-21 after multimedia education of "Pre-intervention anxiety and depression" identification. The data were collected during next appointment/mail/Telephonic follow up. The main objective of post intervention was to measure the mean difference of DASS score against Pre-intervention.

- 9. 2-week Post-Intervention Anxiety, Depression and stress: The parent anxiety, depression and stress were again assessed after two weeks of 'post intervention anxiety depression" identification. The technique of data collection was same as mentioned under Pre and post intervention. The main objective of two-week post intervention was to measure the mean difference DASS score against Post-intervention
- 10. Anxiety, depression and stress mean difference: Finally, mean differences in the anxiety and depression level of parents in both Intervention Group and Control group were measured.

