#### 3.10.1 To Intervention group:

#### **Before chemotherapy:**

- Multimedia Education: The Intervention group received 60 minutes of PowerPoint multimedia education in Urdu language about chemotherapy, its side effect and nutritional guide. The copy of PowerPoint presentation is given in Annexure –III. It was ensured that well explained and comfortable friendly environment was provided to the parents.
- 2. Booklet providence: A booklet "Chemotherapy and you" in Urdu translation were provided to the parents focusing on the detailed information about chemotherapy and its side effects management. The copy of the booklet is enclosed in Annexure –VI.

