## 3.10.2 To control Group:

## **Before chemotherapy:**

They were recruited in the study and were informed about the day of data collection for post-analysis.

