# After Chemotherapy:

Control group followed routine care. During routine care parent verbally educated by the physician and nurses about Chemotherapy and Side effect Management.

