#### **CHAPTER 4: RESULT**

#### 4.1 Participant flow:

Consolidated Standards of Reporting Trials (COSORT) guidelines were used for organization of methods and results of the study [68]. Total 113 children were admitted in Department of Pediatric Oncology at Indus hospital, Karachi from September 2018 to November 2018. Out of 113, 13 parents along with their children were excluded for not meeting inclusion criteria i.e. non-confirmation of cancer diagnosis, no need for Chemotherapy and refused to participate in study. Thus, 100 parents were randomly allocated to intervention group and Control group with equal number of allocations in each group respectively.

Out of 50 parents in intervention group 4.5% (n=9) were lost during follow up, due to death (n=2) of the children and no response (n =7) from parents. In intervention group 4 children were lost in 1st week, 2 were lost in 2nd week, 2 were lost in 3rd week and 1 was lost in 4th week of follow up. On the other hand, 50 parents along with their children who were randomly allocated to control group as routine care, 3 children died, and 11 participants did not respond afterward. Total 6 were lost in 1st week, 4 were lost in 2nd week, 2 were lost in 3rd week and 2 were lost in 4th week of follow up in control group. It was further identified that lost to follow-up due to death and non-response was somewhat more in control groups as compared to intervention group. The detail is mentioned in *Figure 1* 

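### Exclusion criterion 4 (uneasiness during the educational session) can, on its plain reading, be observed only after randomisation, and a session is described only for the intervention arm

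*Combined protocol and SAP*

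**What the plan says.** Section 3.6 has four exclusion criteria. The fourth is "Parents showing uneasiness and discomfort during educational session".

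Section 3.9 gives the order of events. Item 4 reads "In the multimedia room, consent was taken from the parents and they were selected according to the above-mentioned inclusion and exclusion criteria". Item 5 follows: "The parents were allocated to Intervention group and Control group per the generated random number". No educational session is listed between the two. Section 3.8 adds "The participation of each parent in each session was based on the given generated numbers".

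Section 3.10.1 describes the session, before chemotherapy: "The Intervention group received 60 minutes of PowerPoint multimedia education in Urdu language". For controls at the same stage, section 3.10.2 says only "They were recruited in the study and were informed about the day of data collection for post-analysis". After chemotherapy controls had routine care: "During routine care parent verbally educated by the physician and nurses about Chemotherapy and Side effect Management".

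Section 4.1 gives the reasons for the 13 exclusions before allocation as "non-confirmation of cancer diagnosis, no need for Chemotherapy and refused to participate in study", and puts every later loss down to death of the child or no response. The abstract says that those lost to follow-up were left out, so that 77 parents were analysed. Section 3.14 states no rule for analysing parents in the arm to which they were allocated.

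**The concern.** A criterion that depends on behaviour in a session cannot be judged before the session takes place. If the session follows allocation, the criterion is a post-randomisation exclusion presented as an eligibility rule. If only one arm has a session, it can remove parents from that arm alone.

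The trait makes this worse. Uneasiness and discomfort lie close to two of the three DASS-21 outcomes, anxiety and stress. The plan does not define them and does not say who judges them or when. Removing uneasy parents from the intervention arm would select on reaction to the intervention and leave a calmer group to compare with unselected controls. A completer analysis would not bring those parents back.

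**Working it through.** The question is mainly one of timing, so the passages are set in order first. The participant flow is then checked for any trace of the criterion in use.

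**Timing**

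| Step | Place | What happens | Can criterion 4 be observed? |
|---|---|---|---|
| Consent and selection | 3.9 item 4 | All criteria nominally applied | No session has been described yet |
| Allocation | 3.9 item 5 | Parents assigned to arms | No |
| Before chemotherapy, intervention | 3.10.1 | 60-minute multimedia education | Yes |
| Before chemotherapy, control | 3.10.2 | Told the day of data collection | No session described |
| After chemotherapy, control | 3.10.2 | Verbal education in routine care | Only if this counts as a session |

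The session in 3.10.1 is given to parents already identified as the intervention group, so it comes after allocation. The sentence in 3.8 on participation points the same way, although session is not defined there.

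**Flow by reason (section 4.1)**

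- Randomised: 113 - 13 = 100, 50 per arm.
- Intervention losses: 2 deaths + 7 no response = 9, leaving 50 - 9 = 41.
- Control losses: 3 deaths + 11 no response = 14, leaving 50 - 14 = 36.
- Analysed: 41 + 36 = 77, as the abstract states.
- Excluded or lost: 13 + 9 + 14 = 36, all with another stated reason. Reported under criterion 4: 0.

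**Flow by week**

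- Intervention: 4 + 2 + 2 + 1 = 9.
- Control: 6 + 4 + 2 + 2 = 14.

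Both counts close, with nobody left over.

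**Comparison of losses** (50 per arm, two-sided Fisher exact test)

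| | Intervention | Control | p |
|---|---|---|---|
| All losses | 9 (18%) | 14 (28%) | 0.34 |
| No response | 7 (14%) | 11 (22%) | 0.44 |
| Lost in week 1 | 4 | 6 | 0.74 |
| Deaths | 2 | 3 | 1.00 |

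Difference in losses: d = 0.18 - 0.28 = -0.10. The Newcombe interval combines the Wilson limits of each proportion, which are 0.098 to 0.308 for 9/50 and 0.175 to 0.417 for 14/50:

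- Lower: -0.10 - √[(0.18 - 0.098)² + (0.417 - 0.28)²] = -0.26
- Upper: -0.10 + √[(0.308 - 0.18)² + (0.28 - 0.175)²] = +0.07

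No category is higher in the intervention arm. The counts are small and attrition has other causes, so the tests neither prove nor exclude use of the criterion. They show only that the pattern gives no sign of removal confined to the intervention arm.

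**Outer bound.** If removals under criterion 4 had been recorded as no response, which the documents do not suggest, they could number from 0 to 7 of 50 (0% to 14%) in the intervention arm.

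**The case against.** The strongest reply is that the criterion did nothing here. Every exclusion and loss has another stated reason, the counts close, and no reported result changes. This stands for the completed trial, where what remains is a clarification. The rule is still in the eligibility list, however. The text never says that no parent met it, and section 5.3 calls the intervention replicable, so a later study could copy the rule. Figure 1, which may give more detail on flow, is not shown in the available text, so nothing should be inferred from its absence.

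Second, section 3.9 item 4 places selection in the multimedia room before allocation, so the authors may have meant discomfort seen at that encounter. The word session in section 3.8 could also refer to recruitment. Both are possible, which is why the point is limited to the plain reading. The wording of criterion 4 does not say this, and no pre-allocation session is described.

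Third, one-arm operation depends on an undefined term. If the controls' routine verbal education counts as a session, the criterion could act in both arms. That is fair, but the exclusion would still come after randomisation.

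Fourth, the completer analysis is a separate weakness, present with or without criterion 4. This is right. It matters here only because it leaves the risk unguarded.

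**Conclusion.** The point holds as a design risk; bias has not been shown. Sections 3.6 and 3.9 do not fit together: one of the criteria said to be applied before allocation cannot, as worded, be assessed then. Followed as written, it would remove parents after randomisation on a trait close to the outcomes, and in the intervention arm only if that arm's multimedia education is the session meant.

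No size of bias can be estimated from the documents, and none is claimed. Reported use is zero, and losses were numerically higher in control. The conclusion assumes that the educational session is the one in section 3.10.1 and that the reasons in section 4.1 are complete. If the authors meant discomfort at screening, one sentence saying so would resolve the matter.

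**What to change.** **In the plan or any replication.** Remove criterion 4 from the eligibility list and keep only criteria that can be assessed in both arms before allocation. State that a parent who is uneasy in the session, or leaves it, remains in the allocated arm, is followed for DASS-21 at days 14 and 28 unless consent is withdrawn, and is analysed as allocated. This concerns eligibility and analysis only; whether a distressed parent may leave the session is a separate matter and is not affected. The cost is one line in the eligibility list. The downside is that a few parents with incomplete sessions stay in the intervention arm.

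**For the completed trial.** Reconcile section 3.6 with section 3.9 items 4 and 5 by saying when criterion 4 was assessed and in which arms. State in section 4.1 how many parents were removed under it, zero if that is so, or point to Figure 1 if the count is there. Analyse any such parent who has DASS-21 data as allocated. If the count is zero, this costs one or two sentences and no result changes.
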